### **Processing Protocols:**

#### Bone Marrow and Peripheral Blood Processing from EDTA Tubes:

1. Spin the bone marrow (BM) aspirate or peripheral blood (PB) at 2500 rpm (1500 rcf) for 5 minutes to isolate neat plasma prior to adding the PBS/Ficoll.
2. Store 5 x 300uL aliquots of plasma at -80deg C.
3. Add 2 volumes of PBS to the PB/BM and be sure to mix well to ensure a good underlay of the Ficoll.
4. Add a 1:1 volume of Ficoll to the diluted BM/PB by carefully dispensing at the bottom of the conical tube. The BM/PB should lay on top of the Ficoll layer. Try not to mix the Ficoll and BM/PB.
5. Spin the tubes at 3000 rpm (2000 rcf) for 15 minutes.
6. The mononuclear layer interface will lay between the Ficoll and plasma/PBS layers and will often appear whitish if there is a larger number of cells. Carefully remove this interface taking as little Ficoll as possible. If you cannot see the layer, just remove several mL from on top of the Ficoll layer, this will contain all the cell. Dilute the interface containing the cells, with 4 volumes of RPMI (supplemented with 10%FBS, and 1% Pen/Strep). The remaining Ficoll and RBCs at the bottom of the tube can be discarded.
7. Spin the mononuclear cells at 1000rpm for 5 min.
8. Resuspend the cell pellet in 10 to 40ml of RBC Lysis Buffer (ie; Qiagen RBC Lysis Buffer). The volume of lysis buffer depends on the cell pellet. For very small pellets use 10mL, for very large pellets, use 40mL RBC lysis .
9. Resuspend the cells in RPMI (supplemented with 10%FBS, and 1% Pen/Strep) and count the cells using a hemacytometer.
10. Freeze the cells in 10% DMSO, 20% FBS, and 70% RPMI with no more than 10million cells per mL and 1 mL per cryotube. Freeze samples either using a cell freezer container in a -80deg C freezer (i.e.; [name] container) or a controlled rate freezer. Once cells have reached -80deg C, transfer cryotubes to a liquid nitrogen cryounit.

PK Studies, Peripheral Blood Processing from SST Tube

1. Blood samples will be collected by direct venipuncture or through an indwelling catheter. If a catheter is used for blood collection, then approximately 1mL of blood should be withdrawn initially then discarded. Only saline is permitted to keep catheters patent, unless discussed and agreed upon by the Sponsor. If samples are obtained through a heparin lock, sufficient blood (~1mL) must be withdrawn to remove the heparin solution.
2. Immediately after collection, gently invert each tube 5 times and allow blood to clot for 30-45m at room temperature (tube standing upright).
3. Centrifuge samples at 4deg C for 10min (singing buckets) or 15 minutes (fixed buckets) at 100-1300g until clot and serum are well separated. Note: If refrigerated centrifuge is not available, prechill centrifuge tube holders at -20deg C for 20m prior to centrifugation.
4. Transfer 1mL aliquots of serum into 4 appropriately labeled screw cap polypropylene tubes.
5. Store samples at -80deg C until ready for analysis.

PAXgene Tube Storage for BM

1. Tubes will be stored upright at -80deg C until ready for pickup by the [name] Lab.

## **17.11 APPENDIX K: PARTICIPANT MEDICATION DIARY**

Cohort 1 and 2 – Medication Diary

Cycle: \_\_\_\_\_ Participant's ID: \_\_\_\_\_

Instructions:

1. Complete one form for each cycle of treatment.
2. You will take Inqovi once daily on Days 1-5 or Days 1-4, Days 1-3 or Day 1, 3 and 5 depending on the dose level you are assigned,
3. The tablet should be taken on an empty stomach, 2 hours before or 2 hours after meals, and at the same time each day.
4. If a dose of Inqovi is missed within 12 hours of the time it was supposed to be taken, it should be taken as soon as possible. If it is past 12 hours, the dose should not be made up. Extend the dosing period by 1 day for every missed dose to complete the total number of daily doses for each cycle.
5. You will take KPT-8602 once daily on Days 8-12 for all dose levels, and possibly on Days 13-21 or on Days 15-19 depending on the dose level you are assigned, during a 28-day cycle.
6. If a dose of KPT-8602 is missed within 12 hours of the time it was supposed to be taken, it should be taken as soon as possible. If it is past 12 hours, the dose should not be made up. Extend the dosing period by 1 day for every missed dose to complete the total number of daily doses for each cycle.
7. If you vomit after taking a dose of KPT-8602 and/or Inqovi, do not retake the dose. Take the next dose of KPT-8602 and/or Inqovi at the regular schedule.
8. If you miss any doses please contact us.
9. Record the date, the number of tablets that you took, and when you took them. If you miss a dose, please record this also below.
10. If you have any comments or notice any side effects, please record them in the 'comments' column.
11. On the days you are being seen in clinic, you must bring in your medication supply from home; however, you should not take your medication until instructed, as the blood draws must be timed with when you take your medication.
12. Please bring this form and your bottles (even it is empty) when you come for your clinic visits.

Day	Date	Study Drug				Comments	
		KPT-8602		INQOVI			
		Time	# of Tablets	Time	# of Tablets		
1		None	None				
2		None	None				
3		None	None				
4		None	None				

Day	Date	Study Drug				Comments	
		KPT-8602		INQOVI			
		Time	# of Tablets	Time	# of Tablets		
5		None	None				
6		None	None	None	None		
7		None	None	None	None		
8				None	None		
9				None	None		
10				None	None		
11				None	None		
12				None	None		
13				None	None		
14				None	None		
15				None	None		
16				None	None		
17				None	None		
18				None	None		
19				None	None		
20				None	None		
21				None	None		
22		None	None	None	None		
23		None	None	None	None		
24		None	None	None	None		
25		None	None	None	None		
26		None	None	None	None		
27		None	None	None	None		
28				None	None		

**17.12 APPENDIX L: CONTROLLED MEDICATIONS FOR HIV, HEPATITIS B OR HEPATITIS C  
DISEASE CONTROL (CYP SUBSTRATES)**

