### **3.2 DRUG ADMINISTRATION**

Drugs will be self-administered at home except for the days that participants are being seen in clinic for pharmacokinetic blood draws. On those days, participants should be instructed to bring in their medication supply from home, without taking the medication, as they will be instructed when to do so as the blood draws must be timed with drug administration.

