#### **3.2.1 KPT-8602**

KPT-8602 will be dosed per participant assignment and as outlined in Section [3.1.2](#). KPT-8602 tablets are film coated for ease in handling and should be swallowed whole (not crushed). Do not break, crush, or divide the tablets to prevent an increased risk of dermatologic toxicity if the powder comes in contact with skin. Oral KPT-8602 should be taken with or within 30 minutes of eating.

Medication bottles and leftover pills will be collected at the end of each cycle to monitor participant adherence.

Participants will be asked to complete a medication diary ([Appendix K](#)). If a dose is missed within 12 hours of the time it is usually administered, administer the missed dose as soon as possible and then resume the normal daily dosing schedule. Extend the dosing period by 1 day for every missed dose to complete the total number of daily doses for each cycle. If a dose is vomited, do not administer an additional dose (continue with the next scheduled dose).

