#### 14.1.4 Formulation and preparation

Eltanexor is an immediate-release tablet for oral administration. Initial supplies came in 2 strengths: 5 mg and 20 mg of the active pharmaceutical ingredient per tablet. The 20 mg tablet is no longer being used. Current supplies for the clinic are 5 mg and 10 mg tablets, where the 10- mg tablet is weight proportional (2 $\times$ ) with respect to the 5-mg tablet. All inactive ingredients used in the tablets are either compendia or generally recognized as safe. Tablets are film coated for ease of handling. Detailed information related to the manufacturing, components/excipients, packaging, and storage of the drug formulations is provided in the Eltanexor IB.

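### The single participant diary gives one food instruction without naming the drug, and omits the food condition that Section 3.2.1 sets for KPT-8602

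*Combined protocol and SAP*

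**What the plan says.** Section 3.2 of the protocol sets a separate food condition for each drug. For the investigational drug, Section 3.2.1 says "Oral KPT-8602 should be taken with or within 30 minutes of eating". For Inqovi, Section 3.2.2 gives a fasting condition. Sections 14.1.6 and 14.2.5 only refer back to these two sections.

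Appendix K is a single medication diary for Cohorts 1 and 2, with twelve instructions and separate time and tablet-count columns for each drug. The relevant items are:

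- Item 2 gives the Inqovi schedule: "You will take Inqovi once daily on Days 1-5 or Days 1-4, Days 1-3 or Day 1, 3 and 5", according to dose level.
- Item 3 gives the only food instruction on the form: "The tablet should be taken on an empty stomach, 2 hours before or 2 hours after meals, and at the same time each day". The same sentence appears in Section 3.2.2. No drug is named.
- Item 4 covers missed doses of Inqovi, by name.
- Item 5 opens the KPT-8602 schedule: "You will take KPT-8602 once daily on Days 8-12 for all dose levels".
- Items 6 and 7 cover missed KPT-8602 doses and vomiting of either drug, again by name.

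Both products are tablets. Section 14.1.4 says of KPT-8602: "Current supplies for the clinic are 5 mg and 10 mg tablets". On where doses are taken, Section 3.2 says: "Drugs will be self-administered at home except for the days that participants are being seen in clinic for pharmacokinetic blood draws".

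**The concern.** Under the Inqovi heading of Section 3.2.2, the reference to a tablet is clear. As a separate item on a form that covers two tablet drugs, it is not. There are two defects:

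1. Item 3 does not say which drug it governs.
2. The form carries over the KPT-8602 schedule, missed-dose rule and vomiting rule, but not its food condition.

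The second defect stands however item 3 is read.

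What is at stake is control over the conditions in which the investigational drug is taken at home. KPT-8602 pharmacokinetics are a secondary objective in both phases (Section 1.1.2), and exposure-response is an exploratory one (Section 1.1.3). Section 1.2.3.3 intends to use PK, together with other data, to settle dosing in later trials. Section 14.1.7 avoids acid-reducing agents during dose finding because an effect on KPT-8602 PK cannot be excluded, so the protocol already treats conditions of intake as relevant to exposure. A departure from Section 3.2.1 at home would also leave no trace: the diary records time and number of tablets, and Section 5.2.1 records dose and sample times, but neither records food.

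**Working it through.** The check is mainly a comparison of texts. The one piece of arithmetic is a count of doses taken away from the clinic. The plan states no such count, so there is no figure of its own to reproduce first.

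**Text comparison**

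| Drug | Food condition in Section 3.2 | Food condition tied to that drug by name in Appendix K |
|---|---|---|
| Inqovi | Fasting (3.2.2) | None; item 3 has the 3.2.2 wording but names no drug |
| KPT-8602 | With food (3.2.1) | None |

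Food instructions in the diary: 1. Food instructions that name a drug: 0. Food instructions specific to KPT-8602: 0.

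**Cycle 1 doses taken at home**

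Inputs:

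- Planned KPT-8602 doses (Section 3.1.2). Levels 1 and -2: Days 8-12 and 15-19, so 5 + 5 = 10. Levels 2 and -1: Days 8-21, so 14.
- PK draw days that are also dosing days (Section 5.1). Levels 1 and -2: Days 8, 9 and 12. Levels 2 and -1: Days 8, 9 and 21. That is 3 doses in either case. The remaining draw days (13 and 14, or 22 and 23) are not planned dosing days.
- Day 15. This is a clinic visit and a dosing day at every level, and footnote 5 of the cycle 1 calendar (Section 3.5.1) times an ECG at 2 hours after that day's dose. Diary item 11 asks participants to hold their medication on clinic days until instructed. The Day 15 dose may therefore be taken in clinic, although it is not a PK draw day in cycle 1.

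Formula: home doses = planned doses - doses taken in clinic.

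| Levels | Planned | Home, PK days only in clinic | Home, Day 15 also in clinic |
|---|---|---|---|
| 1, -2 | 10 | 10 - 3 = 7 | 10 - 4 = 6 |
| 2, -1 | 14 | 14 - 3 = 11 | 14 - 4 = 10 |

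The home share is thus 60% to 70% at levels 1 and -2, and 71% to 79% at levels 2 and -1. Section 5.2.1.2 keeps the same PK schedule in Phase II, so the count applies there too. After cycle 1 the only scheduled PK draws are on Day 15 of cycles 2 and 3.

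**Size of any exposure change**

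This cannot be computed. The documents give no figure for the effect of food on KPT-8602 exposure, and I have not assumed one.

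**The case against.** The strongest counter-argument is that item 3 is an Inqovi instruction and will be read as one. Items 2 to 4 form an Inqovi block, the tablet is in the singular, the sentence matches Section 3.2.2, and KPT-8602 first appears at item 5. The two drugs have different planned days and separate columns. All of this stands. A reader might infer that the diary directly contradicts Section 3.2.1 by telling participants to take KPT-8602 fasting. The documents do not support that: item 3 is ambiguous and the KPT-8602 condition is missing, but no line orders fasted KPT-8602.

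Second, the diary need not be the only source of instruction. Section 3.4.2 says drug is dispensed each cycle with instruction in self-administration, and that the diary is reviewed at visits. Staff working from Section 3.2.1 could convey the food condition orally. The consent form is not in the text available to me, so it may mention it. This also stands, and it makes fasted home dosing a possibility only. It does not remove the gap, because nothing in the documents describes food counselling for KPT-8602.

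Third, a reader might go on to infer that the PK profiles will misrepresent the exposure behind the DLT, safety and response data. That needs participants to misapply item 3, staff not to correct it, clinic doses to be taken with food, and food to change exposure materially. The documents establish none of these steps. Exposure-response is exploratory and descriptive, and the DLT definition, the Simon two-stage boundaries and the response analysis are not touched.

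**Conclusion.** The point holds as an inconsistency between a participant-facing form and the protocol text. The diary does not tie its one food instruction to a drug and leaves out the condition that Section 3.2.1 sets for KPT-8602. The consequence is that home doses, which are the majority of KPT-8602 doses in cycle 1, may be taken under food conditions other than those in Section 3.2.1, with an unknown effect on exposure.

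This rests on the diary being used as printed. The range in the dose count depends only on where the Day 15 dose is taken; most doses are at home either way. The conclusion takes no position on which food condition is clinically right. It says only that Appendix K must be reconciled with Sections 3.2.1 and 3.2.2.

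**What to change.** Reconcile Appendix K with Sections 3.2.1 and 3.2.2 before the diary is used further:

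- In item 3, name the drug to which Section 3.2.2 assigns that instruction.
- At item 5, repeat the KPT-8602 food condition exactly as Section 3.2.1 states it.

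The cost is two lines on the form, plus whatever review a change to a participant document requires. No visit, assessment or analysis changes. A column for meal times is not needed: no endpoint or analysis in the protocol uses meal times, and it would add recording on every KPT-8602 day.

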**Hepatitis C:**

- Epclusa (sofosbuvir/velpatasvir), Velpatasvir
- Vosevi (sofosbuvir/velpatasvir/voxilapresvir), Velpatasvir
- Zepatier (Elbasvir/grazoprevir)

**Hepatitis B:**

- N/A

**HIV:**

- Efavirenz
- Nevirapine
- Rilpivirine
- Ritonavir
- Dolutegravir
